### **4.3. Decitabine Administration**

Decitabine may be administered by local doctor or at MD Anderson, inclusive of the Regional Cancer Centers (RCC). Commercial supplies of decitabine and will be used and records will be obtained from the local physician as indicated in the Dear Doctor Letter (Appendix E).

### **4.4 Eltrombopag Administration**

4.4.1. Eltrombopag should be taken on an empty stomach (1 hour before or 2 hours after a meal) or with food containing little (<50 mg) or preferably no calcium or dairy products. Allow at least a 4 hour interval between eltrombopag and other medications or products containing polyvalent cations (e.g. calcium, magnesium, aluminum, zinc, selenium or iron) such as antacids, dairy products, and mineral supplements to avoid significant reduction in eltrombopag absorption due to chelation.

4.4.2. Eltrombopag will be self-administered primarily on an outpatient basis; but may be administered as an inpatient. Vomited doses will not be made up on the same day. If the patient misses the dose of eltrombopag in the morning they can take the daily dose no later than 5pm on the same day. Destruction of unused study drug will be in accordance with the institution's drug destruction policy.

4.4.3. Patient compliance will be documented using the MDACC Research Medication Diary and will be assessed at each study visit.

4.4.4 Subjects will be permitted to use HMG-CoA reductase inhibitors (statins) during the study, but these drugs should be used with caution and a 50% dose reduction of the HMG-CoA reductase inhibitor is recommended, with close monitoring for safety, such as liver chemistry and signs and symptoms of myolysis as well as efficacy. Preclinical data showed that eltrombopag is an inhibitor of the organic anion transporters OATP1B1 and BCRP. A clinical drug interaction study to evaluate the impact of eltrombopag on the PK of rosuvastatin, an OATP1B1 and BCRP substrate, was conducted in healthy subjects and identified increased plasma rosuvastatin Cmax and AUC.

4.4.5. Subjects of East Asian ancestry exhibit higher eltrombopag drug exposure and will be initiated at a 50% reduced initial dose.

#### **4.5. Non-MDACC Physician Participation**

4.5.1. Outside physician participation during treatment is acceptable. Documentation of MDACC physician communication with the outside physician will be required. Protocol required evaluations outside MDACC will be documented by telephone, fax or email. Fax and/or email will be dated and signed by the MDACC physician. For protocol required labs that are completed outside MDACC, the PI or treating physician must review results for clinical significance and sign and date results. The screening visit, start of treatment visit (Cycle 1 Day 1), and the end of treatment assessment must be performed at MDACC. MDACC visits must occur at least every 3 months on study, and all study bone marrow assessments should be performed at MDACC.

4.5.2. Changes in decitabine drug dose and/or schedule must be discussed with and approved by the MDACC PI, or their representative prior to initiation, and will be

documented in the patient record. All decisions for dose adjustments of eltrombopag will be made by the MD Anderson treating physician.

4.5.3. All serious adverse events (SAEs) that occur will be reported to the research nurse and will be evaluated by the PI within 48 hours of observing or learning of the event for reportability to the FDA (Appendix E). Fax and/or email will be dated and signed by the MDACC physician.

#### 4.6. Identity of Investigational Product

International Non-proprietary name	eltrombopag
Manufacturer	Novartis Oncology
Dose	100mg daily
Route of Administration	oral
Formulation	12.5mg, 50mg, 75mg and 100mg capsules; in bottle

Eltrombopag will be provided by Novartis Oncology.

For oral administration only
Bottle containing 60 capsules of 100mg eltrombopag.
Store below 30  C (86  F). Do not refrigerate or freeze. Keep bottle tightly closed.
The Expiry date will provided via Certificate of Analysis prepared by Novartis Oncology

#### 4.7. Supportive Care Guidelines

4.7.1. Supportive measures including blood and platelet transfusions, antimicrobials, and analgesics are permitted.

4.7.2. The administration of anticancer therapies, other investigational cytotoxic agents, or prophylactic use of hematopoietic colony stimulating factors are not permitted.

4.7.3. Erythropoietin or hematopoietic colony stimulating factors for treatment of cytopenias are **discouraged**. If administered, the subject will not be eligible for a HI response assessment within one week of the receipt of Procrit or Neupogen, or for one month after receipt of Neulasta or Darbopoetin.

4.7.4. Platelet Transfusions: Platelet transfusion data must be captured on the case report form during the screening, treatment and extension periods. A unit of platelets is

defined as a single unit of platelet-rich plasma or buffy-coat concentrate or 1 apheresis (single donor) concentrate. The number of units transfused must be recorded.

ASCO guidelines suggest platelet transfusion criteria of:

- Platelet count <  $10 \times 10^9/L$  (i.e. severe thrombocytopenia)
- Signs of hemorrhage
- Subject with a high fever and platelet count <  $20 \times 10^9/L$
- Subject has a hyperleukocytosis
- There has been a rapid fall in platelet count and transfusions will not be readily available in case of emergencies

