### 6.2. Study Endpoints

**6.2.1. Primary Efficacy Endpoint:** The overall response rate (CR + PR + HI) based on the IWG-2006 criteria detailed below. Responses must last at least 4 weeks per definition.

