#### Complete Remission:

- Bone marrow:  $\leq 5\%$  myeloblasts with normal maturation of all cell lines
- Persistent dysplasia will be noted
- Peripheral blood
  - o Hemoglobin  $\geq 11\text{g/dL}$
  - o Platelets  $\geq 100 \times 10^9/\text{L}$

- Neutrophils  $\geq 1.0 \times 10^9/L$
- Blasts 0%

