**Partial Remission:**

- All CR criteria if abnormal before treatment except:
  - Bone marrow blasts decreased by  $\geq 50\%$  over pretreatment but still  $> 5\%$

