## 8.3. Analysis of Key Study Endpoints

The primary endpoint is overall response rate (ORR). The ORR will be evaluated along with the exact 95% confidence interval. Secondary endpoints include platelet response, durable platelet response, transformation to AML, incidence of bone marrow fibrosis, and time-to-event outcomes such as progression-free survival (PFS) and overall survival (OS). The probabilities of PFS and OS will be estimated using the method of Kaplan and Meier. The incidence rates of other binary secondary endpoints will be estimated, along with the exact 95% confidence intervals. Subjects that discontinue the study prior to having achieved a clinical response will be considered to have not had an event.

**Patients receiving growth factors other than eltrombopag (erythropoietin, GM-CSF or G-CSF) will not be considered in the HI analysis for the time periods specified in Section 4.5.3 Supportive Care Guidelines. Hemoglobin levels and platelet counts collected from patients that have received a transfusion within the last 7 days will not be considered in the analysis.**

Survival or times to failure and time to progression functions will be estimated using the Kaplan-Meier method. The two-sided log-rank test will be used to assess the differences of time to events between groups.

The total number of dose administrations, the average dose (mg), and the cumulative dose administered will be summarized by eltrombopag treatment group.

Blood chemistry and complete blood counts will be summarized by treatment group at each time point.

Additional exploratory analyses of the key study endpoints will be performed as deemed appropriate.

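### Growth-factor exclusions cover HI only, so hemoglobin or neutrophil counts supported by a growth factor can still establish CR or PR in the primary ORR

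*Combined protocol and SAP*

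**What the plan says.** Section 4.7.2 states that "prophylactic use of hematopoietic colony stimulating factors are not permitted". Section 4.7.3 discourages, but does not forbid, erythropoietin and colony-stimulating factors given to treat cytopenias. If they are given, "the subject will not be eligible for a HI response assessment within one week of the receipt of Procrit or Neupogen"; with the longer-acting products that it names, the bar runs for a month. Section 8.3 carries this into the analysis: patients who received G-CSF, GM-CSF or erythropoietin "will not be considered in the HI analysis for the time periods specified in Section 4.5.3 Supportive Care Guidelines".

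The primary endpoint in section 6.2.1 is CR + PR + HI, and "Responses must last at least 4 weeks per definition"; the HI criteria themselves require 8 weeks. CR needs at most 5% "myeloblasts with normal maturation of all cell lines", together with hemoglobin of at least 11 g/dL, platelets of at least 100 x10^9/L, neutrophils of at least 1.0 x10^9/L and no circulating blasts. PR takes over "All CR criteria if abnormal before treatment except" that marrow blasts fall by at least half but stay above 5%. Neither definition mentions growth factors.

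The only other rule on counts, also in 8.3, sets aside hemoglobin and platelet values within 7 days of a transfusion. It does not cover growth factors or neutrophils.

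**The concern.** The plan accepts that a count taken soon after a growth factor is unsafe evidence of response, but acts on this only for the weakest of the three categories that make up ORR. Hemoglobin and neutrophils, the counts these agents are given to raise, are also thresholds for CR and PR. Read literally, a patient inside the window cannot be assessed for HI but can be recorded as CR or PR on the same blood values.

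At stake are the split between CR/PR and HI and, in some patients, ORR itself. ORR supplies both the headline estimate with its exact 95% interval and the count compared with the futility boundaries. The trial has a single arm, so there is no control group in which the same effect would appear and cancel. The split matters in its own right: section 2.1 puts the CR rate with front-line hypomethylating agents at 6-34%, against 28-70% for ORR.

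**Working it through.** **1. Coverage of the exclusion rules**

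| Response component | Hemoglobin or neutrophil criterion | Growth-factor window | Minimum duration |
|---|---|---|---|
| CR | Hb >= 11 g/dL; neutrophils >= 1.0 x10^9/L | none | 4 weeks |
| PR | as CR, if abnormal before treatment | none | 4 weeks |
| HI | lineage-specific rises | 1 week or 1 month (4.7.3, 8.3) | 8 weeks |

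The gap is therefore in the text.

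**2. Who is exposed.** CR needs platelets >= 100 x10^9/L, and so does PR if platelets were abnormal before treatment. Inclusion criterion 4 admits patients at <= 100, so nearly everyone must gain platelets as well as show the marrow response. The response must also last 4 weeks. One short course of G-CSF before a visit does not meet that, whereas continuing erythropoietin can hold hemoglobin up for that long.

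**3. Would the patient count as HI anyway?** HI-platelet needs a rise of >= 30 from a baseline above 20, or from below 20 to above 20 with at least a doubling, held for 8 weeks.

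- Baseline above 20 and up to 70, reaching 100: the rise is at least 100 - 70 = 30, so the platelet criterion is met.
- Baseline below 20, reaching 100: it is met.
- Baseline of about 71 to 100, just reaching 100: the rise is at most 100 - 71 = 29, so it is not met.
- Any baseline, with a response lasting 4 to 8 weeks: long enough for CR/PR, too short for HI.

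In the first two cases, a response held for 8 weeks changes category and leaves ORR as it is. In the last two, crediting CR/PR adds to ORR. One qualification: the bar in 4.7.3 applies to HI in every lineage, so back-to-back windows would also block HI-platelet. CR/PR would then be the only route to a recorded response.

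**4. Illustration of the futility effect.** First the plan's own figures. With the beta(1.2, 0.8) prior, x responders in n patients give Pr(p < 0.6 | data) = F(0.6; 1.2 + x, 0.8 + n - x), where F is the beta distribution function. Against a fixed 0.6:

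| n | At the boundary | One responder more |
|---|---|---|
| 10 | x = 3: 0.962 | x = 4: 0.878 |
| 20 | x = 8: 0.957 | x = 9: 0.901 |
| 30 | x = 13: 0.963 | x = 14: 0.922 |

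Only the boundary values exceed 0.95, so Table 1 is reproduced. It is reproduced also with the beta(600, 400) comparator (0.961, 0.956, 0.960 at the boundaries).

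An exact binomial recursion through looks at 10, 20 and 30 gives stopping probabilities of 0.971, 0.775, 0.391, 0.105 and 0.015 at true ORR 0.3 to 0.7, which is Table 2.

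Now suppose, as an assumption, that 1 or 2 patients per 40 are recorded as responders only because of supported counts: 1/40 = 0.025 and 2/40 = 0.05.

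| True ORR | Recorded as true | +0.025 | +0.05 |
|---|---|---|---|
| 0.40 | 0.775 | 0.688 | 0.591 |
| 0.50 | 0.391 | 0.299 | 0.220 |

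**5. Cross-reference.** Section 8.3 takes its time periods from 4.5.3. That section begins "All serious adverse events (SAEs) that occur will be reported to the research nurse" and contains no growth-factor periods; these are in 4.7.3. Section 8.3 also names GM-CSF, for which 4.7.3 gives no assessment window.

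**The case against.** The strongest reply is that CR and PR are hard to reach by growth factor alone. The patient needs a marrow response, platelets of at least 100 x10^9/L after enrolling at or below that level, and 4 weeks' duration. Prophylactic colony-stimulating factors are not permitted and therapeutic use is discouraged. Blood counts are weekly until stable, so a brief neutrophil rise would be seen to fade. Many patients who meet all this would also meet HI-platelet. Finally, no section says that supported counts qualify; the plan is silent.

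Most of this stands, and it limits the size. It does not close the gap, because an analyst applying an exclusion worded for HI alone has no basis for withholding CR or PR.

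A reader might infer that every affected patient adds 2.5 points (1/40) to ORR. That is not generally so, because many would already count through HI. A reader might also take a single G-CSF dose before a visit as enough to create a false CR; the 4-week requirement largely prevents that. Nor do the documents support a claim that the futility rule is in fact weakened by the amounts shown, since they give no growth-factor usage rate.

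The wrong section number is clerical: the title given with it, Supportive Care Guidelines, identifies section 4.7.

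**Conclusion.** The point holds in limited form. Sections 4.7.3 and 8.3 keep growth-factor-influenced values out of HI only, so supported hemoglobin or neutrophil counts can satisfy CR or PR within the primary endpoint. The realistic exposure is sustained use, chiefly continuing erythropoietin, in patients who also have the marrow and platelet response. The expected effect is mainly to move patients from HI to CR/PR. ORR rises only where HI would not otherwise be met: for example a baseline platelet count of about 71-100 x10^9/L, a response of 4 to 8 weeks, or HI assessment blocked throughout by the window.

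The size cannot be computed. The fall in stopping probability from 0.391 to 0.299 or 0.220 rests on an assumed one or two extra responders per 40 at a true ORR of 0.50, and is illustration only. The sample size, Table 1 and Table 2 are not in question.

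**What to change.** - Leave the HI bar in 4.7.3 and 8.3 as it is, covering all lineages. Limiting it to the affected lineage would loosen a safeguard already in place.
- Add to both sections: hemoglobin and neutrophil values obtained within the same stated windows may not establish or confirm CR or PR, and the patient stays in the denominator.
- In 8.3, change the reference from 4.5.3 to 4.7.3.
- Reconcile 8.3, which names GM-CSF, with 4.7.3, which gives no assessment window for it.

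The cost is a wording change in two sections. Concomitant medications are already recorded at every scheduled visit (section 5.2), and no design figure changes. The downside is that an occasional CR or PR is confirmed later or not credited. With uninterrupted growth-factor use this could include a patient with a genuine platelet response, because HI is barred in the same windows. The change should be made before responses are adjudicated.

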#### 4.8 Dosing Delays and Dose Modifications

##### 4.8.1. Dose Adjustments for Toxicity:

The doses of eltrombopag and decitabine will be adjusted according to the guidelines shown in the following tables for study drug-related clinically significant toxicity. If toxicity is not covered in the table, doses may be reduced or held at the discretion of the investigator for the patient's safety. See section 4.8.4 for liver chemistry stopping and follow-up criteria.

Patients will be withdrawn from the study if they fail to recover to CTCAE grade 0 to 1 (or within 1 grade of starting values for pre-existing laboratory abnormalities) from a clinically significant non-hematologic treatment-related toxicity within 6 weeks (leading to treatment delay of > 4 weeks) unless the investigator feels that the patient should remain in the study because of evidence that the patient is/may continue deriving benefit from continuing study treatment. Such instances will be discussed with the principal investigator on a case by case basis and the discussion documented in the medical record.

Patients with study-drug related toxicities that are manageable with supportive therapy may not require dose reductions. For patients with other drug-related toxicities, the following dose adjustment rules apply:

NCI CTCAE Grade	Action
Grade 0-2 non-hematological toxicity	No dose reduction.  For grade 2 toxicities that are persistent and/or intolerable (e.g. stomatitis) patients may have a treatment interruption or dose

	reductions to the next lower dose level.
Grade 3-4 clinically significant non-hematological toxicity†	Hold until recover to NCI CTC AE grade 0-1  If recovery occurs within 2 weeks after treatment has been held, dose should be reduced to -1 dose level, if applicable.

† see 4.8.4 for additional liver chemistry stopping and follow-up criteria

## 4.8.2 Decitabine Dosing, Delays and Dose Modifications

4.8.2.1. Decitabine 20mg/m^2 IV on Days 1-5 will be administered for each 28-day cycle.

4.8.2.2. Standard dose reductions for decitabine are described in the following table. Patients with drug-related toxicities that are manageable with supportive therapy may not require dose reductions.

Dose level	Decitabine (in mg/m  for 5 days)
0	20
-1	15
-2	10
-3	10 for 4 days

4.8.2.3. Administration of subsequent cycles should be administered when neutrophils recover to  $\geq 1 \times 10^9/L$  and platelets to  $\geq 30 \times 10^9/L$ , or to baseline levels prior to the start of the last cycle of therapy. Patients with residual disease may start the next cycle with neutrophil and/or platelet counts lower than these if judged to be in the best interest of the patient to start the next cycle. The decision to treat should be documented in the patient's medical record. Patients with delayed recovery of neutrophils to  $1 \times 10^9/L$  and/or platelets to  $75 \times 10^9/L$  in the absence of residual disease may have dose reductions by 1 dose level in subsequent cycles.

4.8.2.4. Patients with serious infectious complications in prior cycles may have the subsequent cycles administered at one dose level reduction in subsequent cycles.

4.8.2.5. Dose reductions and delays of decitabine different than those described above are acceptable after discussion with the investigator, and will require documentation of the rationale for such action.

### 4.8.3 Eltrombopag Dosing Delays and Dose Modifications

Dose modifications for eltrombopag:

Dose level	eltrombopag (mg/day)
+2	300
+1	200
0	100
-1	50
-2	25

#### 4.8.3.1. Starting Dose

The starting dose for all study patients (with the exception of East Asians, see 4.8.3.2.) will be 100mg orally daily. East Asians will start at 50mg orally daily.

#### 4.8.3.2. Dose Adjustments for Platelet Count:

The dose of eltrombopag can be increased every 2 weeks by 100mg until a maximum of 300mg per day has been attained. Dose adjustments will be dependent on each subject's platelet counts; adjusted to maintain an un-transfused platelet count  $>100 \times 10^9/L$ . Laboratory work including a CBC with differential and blood chemistries must be evaluated weekly for 4 weeks after any change in eltrombopag dosing.

All decisions for dose adjustments of eltrombopag will be made by the MD Anderson treating physician. If needed, additional supplies of eltrombopag may be mailed by the MD Anderson research pharmacy to the patient.

Eltrombopag will be held if platelet counts exceed  $400 \times 10^9/L$ , and will be resumed the next scheduled day that platelet counts have decreased to  $\leq 100 \times 10^9/L$ . Dose should be reduced to the next lower dose level, if appropriate.

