#### 4.8.3.3. Dose Adjustments for Subjects of East Asian Ancestry:

The starting dose for patients of East Asian ancestry will be 50mg orally daily. East Asian (i.e. Japanese, Chinese, Taiwanese and Korean) subjects exhibited 50-55% higher eltrombopag plasma concentrations compared to non-East Asian subjects. Dose adjustments for platelet counts will proceed as per 4.8.3.1. regardless of ethnicity.

Dose reductions different than the dose described above are acceptable after discussion with the sponsor and the PI, and will require documentation of the rationale for such action.

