#### 4.8.4. Liver Chemistry Stopping and Follow-Up Criteria:

Treatment should be held for any of the following liver chemistry criteria:

1. ALT  $\geq 5x$  ULN and bilirubin  $\geq 2.7x$  ULN ( $>35\%$  direct bilirubin)

2. ALT  $\geq$  8x ULN
3. ALT  $\geq$  5x ULN but  $<$  8x ULN and persists for  $\geq$  2 weeks
4. ALT  $\geq$  5x ULN if associated with the appearance or worsening of symptoms of hepatitis such as nausea, vomiting, right upper quadrant pain or tenderness.
5. ALT  $\geq$  5x ULN but  $<$  8x ULN and cannot be monitored weekly for  $\geq$  2 weeks.

When any of the above criteria is met, do the following:

- Immediately withdraw investigational product

Report the event to Novartis Oncology

- within 24 hours of learning of its occurrence
- Complete the SAE data collection tool if the event also meets the criteria for an SAE. All events of ALT  $\geq$  5x ULN and bilirubin  $\geq$  2.7x ULN ( $>$ 35% direct bilirubin), modified Hy's Law for oncology clinical trials, must be reported as an SAE.

NOTE: if serum bilirubin fractionation is not immediately available, study drug should be discontinued if ALT  $\geq$  5x ULN and bilirubin  $\geq$  2.7x ULN. Serum bilirubin fractionation should be performed if testing is available. If testing is unavailable, record the presence of detectable urinary bilirubin on dipstick, indicating bilirubin elevation and suggesting liver injury.

- Hold eltrombopag until recovery to NCI CTC AE grade 0-1 and restart at next lower dose level regardless of recovery time.

In addition, for #1:

- Make every reasonable attempt to have subjects return to clinic within 24 hours for repeat liver chemistries, liver event follow-up assessments (see below) and close monitoring.
- A specialist or hepatology consultation is recommended.
- Monitor subjects twice weekly until liver chemistries (ALT, AST, alkaline phosphatase, bilirubin) resolve, stabilize or return to within baseline values.

For #2, 3, 4, 5:

- Make every reasonable attempt to have subjects return to clinic within 24-72 hours for repeat liver chemistries and liver event follow-up assessments (see below)
- Monitor subjects weekly until liver chemistries (ALT, AST, alkaline phosphatase, bilirubin) resolve, stabilize or return to within baseline values.

For all Criteria 1-5, make every attempt to carry out the liver event follow-up assessments described below as clinically appropriate:

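### The fixed 100 mg eltrombopag escalation step does not match the listed dose levels below 100 mg, so one step after a reduction can pass the dose at which the event occurred

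*Combined protocol and SAP*

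**What the plan says.** The table in 4.8.3 lists five eltrombopag levels: 25 mg (level -2), 50 mg (-1), 100 mg (0), 200 mg (+1) and 300 mg (+2). Section 4.8.3.1 starts patients at 100 mg, and East Asian patients at 50 mg.

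Upward moves have a single rule, in 4.8.3.2: "The dose of eltrombopag can be increased every 2 weeks by 100mg until a maximum of 300mg per day has been attained". The aim is an untransfused platelet count above 100 x 10^9/L. Section 4.8.3.3 applies the same titration to East Asian patients: "Dose adjustments for platelet counts will proceed as per 4.8.3.1. regardless of ethnicity".

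Downward moves go by level. After a hold for platelets above 400 x 10^9/L, 4.8.3.2 says: "Dose should be reduced to the next lower dose level, if appropriate". After a liver event, 4.8.4 says: "Hold eltrombopag until recovery to NCI CTC AE grade 0-1 and restart at next lower dose level regardless of recovery time". For Grade 3-4 non-hematologic toxicity, 4.8.1 says: "If recovery occurs within 2 weeks after treatment has been held, dose should be reduced to -1 dose level, if applicable".

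Section 4.8 has no rule on re-escalating after a reduction, and none that ties later doses to the dose at which the event occurred.

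**The concern.** Going up is defined in milligrams and going down in table levels. The levels are 100 mg apart only from 100 mg upward; below that the gaps are 50 mg (50 to 100) and 25 mg (25 to 50). One upward step from a low dose therefore covers more ground than the reduction that put the patient there.

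Two things follow. First, patients can land on doses that are not in the table, and the instruction to go to the next lower level then has no defined answer. Second, one permitted increase can take a patient past the dose at which a liver event or an excessive platelet count occurred. This is not confined to East Asian patients: it applies to anyone reduced from the standard 100 mg start.

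Re-escalation is a realistic path. Entry requires platelets of at most 100 x 10^9/L, and titration aims above that. After a hold for counts above 400, drug resumes only at 100 or below, so the patient restarts with the target unmet.

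**Working it through.** **Inputs.** Listed levels 25, 50, 100, 200, 300 mg (4.8.3). Step +100 mg every 2 weeks, maximum 300 mg (4.8.3.2). Starts of 100 mg and 50 mg (4.8.3.1). Reduction by one listed level (4.8.3.2, 4.8.4).

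**Check 1: does the step reproduce the table?** Add 100 mg from each starting point, in whole steps, without passing 300 mg.

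| From | Doses reached | Not listed | Next whole step |
|---|---|---|---|
| 100 mg | 200, 300 | none | 400 (over maximum) |
| 50 mg | 150, 250 | 150, 250 | 350 (over maximum) |
| 25 mg | 125, 225 | 125, 225 | 325 (over maximum) |

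The standard path of 100, 200, 300 mg is reproduced exactly. From 50 or 25 mg every dose reached is off the table. The maximum can be reached only by shortening the last step, which the text does not describe.

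**Check 2: first step after a reduction.** Ratio = (next lower listed level + 100) / dose at the event.

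| Event dose | Reduced to | After one step | Ratio |
|---|---|---|---|
| 50 mg | 25 mg | 125 mg | 125/50 = 2.5 |
| 100 mg | 50 mg | 150 mg | 150/100 = 1.5 |
| 200 mg | 100 mg | 200 mg | 200/200 = 1.0 |
| 300 mg | 200 mg | 300 mg | 300/300 = 1.0 |

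First-step overshoot is limited to events at 50 or 100 mg. I give no ratio for events at 150 or 250 mg, because the protocol does not say which level lies below an unlisted dose. These are dose ratios and need no pharmacokinetic assumption.

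**Check 3: would stepping by listed level be enough?** The paths become 25, 50, 100, 200, 300 and 50, 100, 200, 300. One level down and one level up returns to the event dose, so every first-step ratio is 1.0. A second step still passes it: event at 100 mg, then 50, 100, 200 mg, which is 200/100 = 2.0 times. For an event at 200 mg the path is 100, 200, 300 mg, or 300/200 = 1.5 times, under either rule. The step change removes only the first-step overshoot; a limit on re-escalation is needed for the rest.

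**The case against.** The strongest reply is that the dose is controlled by people rather than by the step. Increases are permitted, not required. The treating physician at the centre makes every dose decision. Blood counts and chemistries are weekly for 4 weeks after any change. Section 2.3.1 advises against reinitiating after discontinuation for hepatotoxicity; where the drug is restarted, it asks for caution, weekly liver tests during dose adjustment, and permanent discontinuation if abnormalities persist, worsen or recur. All of this stands and bounds the risk. None of it sets the size of the step, and 4.8.4 itself directs a restart. The clause in 4.8.3.3 allowing documented departures covers reductions, not increases.

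It is also fair to say that an unlisted dose is not a prohibited one. Section 2.2 allows 25 to 300 mg according to platelet response, and the capsule strengths in 4.6 can make up 125, 150, 225 and 250 mg. What remains is the undefined next lower level.

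Three stronger readings are tempting but not supported:

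- A reader might infer that the common step overexposes East Asian patients, since these "subjects exhibited 50-55% higher eltrombopag plasma concentrations compared to non-East Asian subjects". Comparing exposure at different doses needs dose-proportionality or some other assumed relation, which the documents do not give, and titration here is to platelet count.
- A reader might infer that 300 mg is an error for East Asian patients, because 2.2 reports a 150 mg maximum for them in two supporting studies. Section 4.8.3.3 applies the rule irrespective of ethnicity as an explicit choice. Whether to cap at 150 mg is a clinical question.
- A reader might take 4.8.1 literally and conclude that a patient on 50 mg gets no reduction for Grade 3-4 toxicity. Read that way, the row would also raise a patient from 25 to 50 mg, which is no reduction. One level down is the natural meaning, so the wording is an editorial matter.

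**Conclusion.** The mismatch is real and follows from the text alone. Below 100 mg the escalation step and the reduction levels do not fit together. The consequences are unlisted doses of 125, 150, 225 and 250 mg, and a first step after reduction that can reach 1.5 times the event dose (event at 100 mg) or 2.5 times (event at 50 mg). The ratios assume that the physician reduces by one listed level and then takes the full permitted step. After platelets above 400 x 10^9/L the reduction is itself conditional on being appropriate.

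This is a dosing-safety gap of moderate weight, bounded by the safeguards above. Standard titration from 100 mg is internally consistent. A reader might infer that the efficacy result is compromised; it is not, because the ORR analysis, its confidence interval and both sets of stopping boundaries do not depend on the step. It is worth correcting because the correction is cheap.

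**What to change.** 1. In 4.8.3.2, replace the fixed 100 mg increase with an increase of one listed dose level (25, 50, 100, 200, 300 mg).
2. In the same section, add that after a reduction for toxicity or for platelets above 400 x 10^9/L the dose is not raised above the dose at which the event occurred, unless the PI agrees and the reason is documented.
3. Editorial: in the 4.8.1 Grade 3-4 row, say that the dose falls by one level. In 4.8.3.3, point to 4.8.3.2 instead of 4.8.3.1; in 4.8.3.1, point to 4.8.3.3 for the East Asian exception.
4. Ask the sponsor whether East Asian patients should be capped at 150 mg. If so, list 150 mg as their top level; if not, a sentence of rationale in 2.2 would help.

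**Cost.** A few lines of text, with no new visits or data beyond documenting exceptions. Escalation from 100 mg is unchanged unless a prior event limits it. From 50 mg, patients receive 100 and 200 mg at weeks 2 and 4 instead of 150 and 250 mg; 300 mg comes at week 6 either way, if the last step is now shortened. From 25 mg the path is 50, 100, 200 and 300 mg at weeks 2, 4, 6 and 8, instead of 125, 225 and 300 mg at weeks 2, 4 and 6 (same assumption). Platelet response may be slower in these patients. The limit in item 2 may also hold some patients at a lower dose.
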